12.4 INSPECTION OF RECORDS

Investigators and institutions involved in the study will permit trial related monitoring and audits on behalf of the sponsor, REC review, and regulatory inspection(s). In the event of an audit or monitoring, the Investigator agrees to allow the representatives of the sponsor direct access to all study records and source documentation. In the event of regulatory inspection, the Investigator agrees to allow inspectors direct access to all study records and source documentation.

12.5 RISK ASSESSMENT

An independent risk assessment will be performed by an ACCORD Clinical Trials Monitor to determine if monitoring is required and if so, at what level. An independent risk assessment will also be carried out by the ACCORD Quality Assurance Group to determine if an audit should be performed before/during/after the study and if so, at what locations and at what frequency.

12.6 BENEFIT/RISK BALANCE

12.6.1 Benefits

Patients may benefit from the treatment intervention. The benefits of ticagrelor in addition to standard medical therapy may include a reduction in the consequences and progression of coronary artery disease. In the PLATO trial [Wallentin *et al*, 2009], there appeared to be an ongoing and continuous improvement in outcomes beyond three months of an acute coronary syndrome. Ticagrelor may therefore have important ongoing secondary preventative benefits even in patients with apparently stable coronary artery disease. This is the rationale for the ongoing trial of the prevention of cardiovascular events in patients with prior myocardial infarction using ticagrelor compared with placebo on a background of aspirin: the PEGASUS trial (NCT01225562).

Patients may also benefit from additional procedures and investigations that they will undergo as part of the study. This will include closer medical supervision and non-invasive imaging investigations that may identify important incidental findings.

12.6.2 Risks

The risks of ticagrelor principally relate to bleeding, transient bradyarrhythmias and dyspnoea. As with most anti-thrombotic treatments, there is a risk of excess bleeding. The incidence of excess major bleeding was modest and we will ensure robust exclusion criteria to prevent inclusion of patients at risk of bleeding. Bradyarrhythmias have been described but are generally transient and do not require intervention. We will record 12-lead electrocardiograms at subject visits and question patients regarding symptoms of dizziness and syncope. For

dyspnea, there is a 14% rate of breathlessness associated with ticagrelor in the PLATO trial [Wallentin *et al*, 2009]. However, again this is usually mild and self-limiting, and discontinuation of study medication was necessary in only 1% of patients.

There are some potential hazards of the non-invasive investigations that we will perform as part of the trial. The main issues relate to exposure to ionising radiation and contrast agent administration. We have a well-developed protocol for cardiac positron emission and computed tomography imaging that minimizes radiation exposure and has clear procedures for managing adverse contrast reactions. We anticipate that the total research protocol dose (TRPD) radiation exposure will be 30 mSv. The TRPD includes radiation exposure from both the PET and CT scans combined. The estimated associated risk of developing fatal cancer is proportional to dose. Using a risk of 5% per Sv [ARSAC Notes] in a healthy population in this age group the estimated associated risk of developing fatal cancer as a result of this exposure is in the region 1 in 650. This risk can be classified as moderate. It is likely that in a population of any patients in the age group 40-50 years the cancer risk is approximately 5% per Sv (and correspondingly less than 5% per Sv as age increases above 50 years). For comparison the average annual background radiation dose arising from natural sources of ionising radiation in the environment in the UK is 2.2 mSv. The TRPD of 30 mSv incurred in this study is approximately 13-14 times annual background radiation from natural sources. An objective of this study is to assess reproducibility of NaF PET/CT. A subgroup of 80 subjects will receive a second PET/CT and additional CT coronary angiogram. This increases the TRPD to 46 mSv in those subjects that have their repeat scan at the randomisation visit, 3 months or 6 months and to 38mSv in those that undergo their repeat scan at 12 months. The associated risk of developing cancer as a result of this exposure is in the region of 1 in 450. This risk can be classified as moderate. A TRPD of 46 mSv is approximately 21 times annual background radiation from natural sources in the UK. All subjects will have two CT coronary angiograms and those in the sub-studies returning at the randomisation visit, 3 months or 6 months will have 3 CT coronary angiograms. We note that in occasional individual cases the effective dose from CT coronary angiography may increase to approximately 20 mSv, if the subject's heart rate cannot be kept sufficiently low, requiring an alternative retrospective gating technique to be used. This will add approximately 12 mSv to the total research protocol dose for all subjects having CTCA.

This can be compared with other commonly used cardiovascular imaging techniques, such as nucleotide myocardial perfusion imaging (15-20 mSv) and diagnostic coronary angiography (7 mSv) [Einstein *et al*, 2007]. The risks of exposure to the contrast medium include allergic reactions and impairment of kidney function. Amongst patients with moderate-to-severe chronic kidney disease, there is a 2-4% risk of kidney impairment after computed tomography angiography [Barrett *et al*, 2006]. The risk of contrast exposure in this study will be minimised by exclusion of high-risk patients who have significant kidney disease (estimated glomerular filtration rate <30 mL/min/1.73m²).

12.7 STUDY MONITORING AND AUDIT

An ACCORD Clinical Trials Monitor or an appointed monitor will visit the Investigator site prior to the start of the study and during the course of the study if required, in accordance with the monitoring plan if required. Risk assessment will determine if audit, by the ACCORD QA group, is required. Details will be captured in an audit plan. Audit of Investigator sites, study management activities and study collaborative units, facilities and 3rd parties may be performed.

13 GOOD CLINICAL PRACTICE

13.1 ETHICAL CONDUCT

The study will be conducted in accordance with the principles of the International Conference on Harmonisation Tripartite Guideline for Good Clinical Practice (ICH GCP).

A favorable ethical opinion will be obtained from the appropriate REC and local R&D approval will be obtained prior to commencement of the study.

13.2 REGULATORY COMPLIANCE

The study will not commence until a Clinical Trial Authorisation (CTA) is obtained from the appropriate Regulatory Authority. The protocol and study conduct will comply with the Medicines for Human Use (Clinical Trials) Regulations 2004, as amended.

13.3 INVESTIGATOR RESPONSIBILITIES

The Investigator is responsible for the overall conduct of the study at the site and compliance with the protocol and any protocol amendments. In accordance with the principles of ICH GCP, the following areas listed in this section are also the responsibility of the Investigator. Responsibilities may be delegated to an appropriate member of study site staff.

13.3.1 Informed Consent

The Investigator is responsible for ensuring informed consent is obtained before any protocol specific procedures are carried out. The decision of a participant to participate in clinical research is voluntary and should be based on a clear understanding of what is involved.

Participants must receive adequate oral and written information – appropriate Participant Information and Informed Consent Forms will be provided. The oral explanation to the participant will be performed by the Investigator or qualified delegated person, and must cover all the elements specified in the Participant Information Sheet and Consent Form.

The participant must be given every opportunity to clarify any points they do not understand and, if necessary, ask for more information. The participant must be given sufficient time to consider the information provided. It should be emphasised that the participant may withdraw their consent to participate at any time without loss of benefits to which they otherwise would be entitled.

The participant will be informed and agree to their medical records being inspected by regulatory authorities and representatives of the sponsor(s) but understand that their name will not be disclosed outside the hospital.

The Investigator or delegated member of the trial team and the participant will sign and date the Informed Consent Form(s) to confirm that consent has been obtained. The participant will receive a copy of this document and a copy filed in the Investigator Site File (ISF) and participant's medical notes.

13.3.2 Study Site Staff

The Investigator must be familiar with the IMP, protocol and the study requirements. It is the Investigator's responsibility to ensure that all staff assisting with the study are adequately informed about the IMP, protocol and their trial related duties.

13.3.3 Data Recording

The Principle Investigator is responsible for the quality of the data recorded in the CRF at each Investigator Site. The source data plan identifies which source data correspond to CRF data and states which data are recorded directly into the CRF.

13.3.4 Investigator Documentation

Prior to beginning the study, each Investigator will be asked to provide particular essential documents to the ACCORD Research Governance & QA Office, including but not limited to:

- An original signed Investigator's Declaration (as part of the Clinical Trial Agreement documents);

- Curriculum vitae (CV) signed and dated by the Investigator indicating that it is accurate and current.

The ACCORD Research Governance & QA Office will ensure all other documents required by ICH GCP are retained in a Trial Master File (TMF), where required, and that appropriate documentation is available in local ISFs.

13.3.5 GCP Training

All study staff must hold evidence of appropriate GCP training.

13.3.6 Confidentiality

All laboratory specimens, evaluation forms, reports, and other records must be identified in a manner designed to maintain participant confidentiality. All records must be kept in a secure storage area with limited access. Clinical information will not be released without the written permission of the participant. The Investigator and study site staff involved with this study may not disclose or use for any purpose other than performance of the study, any data, record, or other unpublished, confidential information disclosed to those individuals for the purpose of the study. Prior written agreement from the sponsor or its designee must be obtained for the disclosure of any said confidential information to other parties.

13.3.7 Data Protection

All Investigators and study site staff involved with this study must comply with the requirements of the Data Protection Act 1998 with regard to the collection, storage, processing and disclosure of personal information and will uphold the Act's core principles. Access to collated participant data will be restricted to those clinicians treating the participants, representatives of the sponsor(s) and representatives of regulatory authorities.

Computers used to collate the data will have limited access measures via user names and passwords.

Published results will not contain any personal data that could allow identification of individual participants.

14 STUDY CONDUCT RESPONSIBILITIES

14.1 PROTOCOL AMENDMENTS

Any changes in research activity, except those necessary to remove an apparent, immediate hazard to the participant in the case of a urgent safety measure, must be reviewed and approved by the Chief Investigator.

Amendments to the protocol must be submitted in writing to the appropriate REC, Regulatory Authority and local R&D for approval prior to participants being enrolled into an amended protocol.

14.2 PROTOCOL VIOLATIONS AND DEVIATIONS

Prospective protocol deviations, i.e. protocol waivers, will not be approved by the sponsors and therefore will not be implemented, except where necessary to eliminate an immediate hazard to study participants. If this necessitates a subsequent protocol amendment, this should be submitted to the REC, Regulatory Authority and local R&D for review and approval if appropriate.

Protocol deviations will be recorded in a protocol deviation log and logs will be submitted to the sponsors every 3 months. Each protocol violation will be reported to the sponsor within 3 days of becoming aware of the violation.

14.3 SERIOUS BREACH REQUIREMENTS

A serious breach is a breach which is likely to effect to a significant degree:

- (a) the safety or physical or mental integrity of the participants of the trial; or
- (b) the scientific value of the trial.

If a potential serious breach is identified by the Chief investigator, Principal Investigator or delegates, the co-sponsors ([contact]) must be notified within 24 hours. It is the responsibility of the co-sponsors to assess the impact of the breach on the scientific value of the trial, to determine whether the incident constitutes a serious breach and report to regulatory authorities and research ethics committees as necessary.

14.4 STUDY RECORD RETENTION

All study documentation will be kept for a minimum of 5 years from the protocol defined end of study point. When the minimum retention period has elapsed, study documentation will not be destroyed without permission from the sponsor.

14.5 END OF STUDY

It is anticipated that the study will last 3 years: two years for recruitment and one year of follow-up. The end of study is defined as the last participant's last visit.

The Investigators and/or the trial steering committee and/or the co-sponsor(s) have the right at any time to terminate the study for clinical or administrative reasons.

The end of the study will be reported to the REC, Regulatory Authority, R&D Office(s) and co-sponsors within 90 days, or 15 days if the study is terminated prematurely. The Investigators will inform participants of the premature study closure and ensure that the appropriate follow up is arranged for all participants involved. End of study notification will be reported to the co-sponsors via email to [contact].

In accordance with ACCORD SOP CR011, a Clinical Study Report (CSR) will be provided to the Sponsor ([contact]) and REC within 1 year of the end of the study.

Upon completion of the study, the Investigator will upload clinical trial results onto the EudraCT database on behalf of the Sponsor.

14.6 CONTINUATION OF DRUG FOLLOWING THE END OF STUDY

The study medication will not be continued at the trial conclusion as it is not currently licensed for use in stable coronary artery disease. Patients will remain eligible to use ticagrelor for any approved indication however (i.e. for 12 months following an acute coronary syndrome).

14.7 INSURANCE AND INDEMNITY

The co-sponsors are responsible for ensuring proper provision has been made for insurance or indemnity to cover their liability and the liability of the Chief Investigator and staff.

The following arrangements are in place to fulfil the co-sponsors' responsibilities:

- The Protocol has been designed by the Chief Investigator and researchers employed by the University and collaborators. The University has insurance in place (which includes no-fault compensation) for negligent harm caused by poor protocol design by the Chief Investigator and researchers employed by the University.
- Sites participating in the study will be liable for clinical negligence and other negligent harm to individuals taking part in the study and covered by the duty of care owed to them by the sites concerned. The co-sponsors require individual sites participating

in the study to arrange for their own insurance or indemnity in respect of these liabilities.

- Sites which are part of the United Kingdom's National Health Service will have the benefit of NHS Indemnity.
- Sites outside the United Kingdom will be responsible for arranging their own indemnity or insurance for their participation in the study, as well as for compliance with local law applicable to their participation in the study.
- The manufacturer supplying IMP has accepted limited liability related to the manufacturing and original packaging of the study drug and to the losses, damages, claims or liabilities incurred by study participants based on known or unknown Adverse Events which arise out of the manufacturing and original packaging of the study drug, but not where there is any modification to the study drug (including without limitation re-packaging and blinding).

15 REPORTING, PUBLICATIONS AND NOTIFICATION OF RESULTS

15.1 AUTHORSHIP POLICY

Ownership of the data arising from this study resides with the study team. On completion of the study, the study data will be analysed and tabulated, and a clinical study report will be prepared in accordance with ICH guidelines.

15.2 PUBLICATION

The clinical study report will be used for publication and presentation at scientific meetings. Investigators have the right to publish orally or in writing the results of the study.

Summaries of results will also be made available to Investigators for dissemination within their clinics (where appropriate and according to their discretion).

15.3 PEER REVIEW

The study protocol and outcomes data have been reviewed by AstraZeneca who have agreed to help support the conduct and part funding of this clinical trial. There is additional peer review from the Trial Steering Committee and the Edinburgh Clinical Trials Unit statistician as well as the Medical Research Council.

## 2 List of Abbreviations

CI	Confidence Interval
CONSORT	Consolidated Standards of Reporting Trials
DIAMOND	Trial acronym for 'Dual antiplatelet therapy to Inhibit coronary Atherosclerosis and Myocardial injury in patients with Necrotic high-risk coronary plaque Disease'
DMC	Data Monitoring Committee
ECTU	Edinburgh Clinical Trials Unit
hsTnI	High Sensitivity Cardiac Troponin I
N	Number of patients with an observation
SAP	Statistical Analysis Plan
SD	Standard Deviation
SOP	Standard Operating Procedure

## 3 Introduction

This document details the criteria to be used for the definition of the analysis populations and the statistical methodology for analysis for the DIAMOND trial, a randomised trial of Ticagrelor to reduce markers of myocardial injury in patients with stable coronary heart disease and high-risk coronary atheroma. This document has been compiled according to the Edinburgh Clinical Trials Unit (ECTU) standard operating procedure (SOP) "Statistical Analysis Plans" and has been written based on information contained in the study protocol version 5.0, dated 31 January 2017.

DIAMOND is a single centre, randomised, parallel-group, double blind, placebo-controlled trial. Randomisation is at the individual level with a 1:1 allocation ratio, and is minimised on age, gender, baseline plasma troponin concentration, presence of coronary 18F-fluoride uptake (as detailed in the Randomisation System Description document). Patients are randomised to either Ticagrelor or matched placebo tablets. The aim is to recruit 220 patients, with a view to having 55 per group in the group with increased coronary 18F uptake.

## 4 Statistical Methods Section from the Protocol

### 9.2.1 Description of Analysis Sets

*The primary analysis will be to determine whether ticagrelor will reduce plasma high-sensitivity troponin concentrations compared with placebo in patients with stable coronary heart disease and increased coronary 18F-fluoride uptake. For this primary analysis, we will exclude any patient who does not have a blood sample for estimation of the one-month plasma troponin concentration or whose compliance is deemed inadequate (as estimated from pill counts). The required level of medication compliance will be described in the statistical analysis plan.*

### 9.2.2 Methods of Statistical Analysis

*For the primary analysis, the change in plasma high-sensitivity troponin concentration from baseline to 30 days will be compared between the two treatment groups (ticagrelor and placebo) using linear regression, adjusting for the minimisation variables, in patients with coronary 18F-fluoride uptake. Prior to analysis, tests for normality will be undertaken and, where data are skewed, logarithmic transformation will be considered prior to analysis. Effect sizes and 95% confidence intervals will be calculated. Similar analyses will be performed for the assessment of troponin at 30 days in patients without coronary 18F-fluoride uptake, and in the study population as a whole; for troponin at 1 year; and for calcium score and plaque volume at 1 year at the site of baseline coronary 18F-fluoride uptake.*

*Statistical analysis will be performed using SAS. A two-sided  $P<0.05$  will be taken as statistically significant. A full statistical analysis plan will be documented prior to data base lock. This will be overseen by the trial statistician in the Edinburgh Clinical Trials Unit.*

## 5 Description of analysis datasets

The analysis datasets are detailed below. All analyses will be performed on the per protocol population unless otherwise specified.

**Per protocol** we will exclude any patient who does not have a blood sample for estimation of the plasma troponin concentration or whose compliance is deemed inadequate (as estimated from pill counts) at the 30 day visit. Inadequate compliance is defined as <80% using the formula in Section 7.3. Patients will be analysed according to treatment received.

**Safety** the Ticagrelor group will include all subjects who received any Ticagrelor study medication, regardless of the group they were originally allocated to. The placebo group will include all patients who received some study medication, but where all of this was placebo, regardless of the group they were originally allocated to. The group who were randomised but did not receive any medication at all will be reported separately.

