5.4 INELIGIBLE AND NON-RECRUITED PARTICIPANTS

Ineligible and non-recruited patients will receive standard medical care. An anonymised log will be kept of patients who were screened for the study and subsequently found to be ineligible or not recruited.

5.5 PROCEDURES FOR HANDLING SUBJECTS INCORRECTLY ENROLLED, RANDOMISED OR INITIATED ON INVESTIGATIONAL MEDICINAL PRODUCT

Patients incorrectly randomized to the wrong treatment group will be maintained on allocated therapy unless blinding has been compromised. Given that this is a mechanistic study and not a clinical endpoint trial, they will be assigned to the treatment they actually received as part of

the statistical analysis. Records will be kept of the treatment they were originally assigned to, and the treatment they received.

After the first 30 and 90 patients have been randomized into the trial, ECTU will check to ensure that minimization has achieved matching of the two treatment groups.

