9.2 PROPOSED ANALYSES

9.2.1 Description of Analysis Sets

The primary analysis will be to determine whether ticagrelor will reduce plasma high-sensitivity troponin concentrations compared with placebo in patients with stable coronary heart disease and increased coronary ¹⁸F-fluoride uptake. For this primary analysis, we will exclude any patient who does not have a blood sample for estimation of the one-month plasma troponin concentration or whose compliance is deemed inadequate (as estimated from pill counts). The required level of medication compliance will be described in the statistical analysis plan.

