9.2.2 Methods of Statistical Analysis

For the primary analysis, the change in plasma high-sensitivity troponin concentration from baseline to 30 days will be compared between the two treatment groups (ticagrelor and placebo) using linear regression, adjusting for the minimisation variables, in patients with coronary ¹⁸F-fluoride uptake. Prior to analysis, tests for normality will be undertaken and, where data are skewed, logarithmic transformation will be considered prior to analysis. Effect sizes and 95% confidence intervals will be calculated. Similar analyses will be performed for the assessment of troponin at 30 days in patients without coronary ¹⁸F-fluoride uptake, and in the study population as a whole; for troponin at 1 year; and for calcium score and plaque volume at 1 year at the site of baseline coronary ¹⁸F-fluoride uptake.

Statistical analysis will be performed using SAS. A two-sided $P<0.05$ will be taken as statistically significant. A full statistical analysis plan will be documented prior to data base lock. This will be overseen by the trial statistician in the Edinburgh Clinical Trials Unit.

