## 6 Overall statistical principles

All applicable statistical tests will be 2-sided and will be performed using a 5% significance level. Two-sided 95% confidence intervals (CIs) will be presented. All analyses are seeking to show a difference, rather than equivalence or non-inferiority.

In general terms, categorical data will be presented using counts and percentages, whilst continuous variables will be presented using the mean, standard deviation (SD), median, lower quartile, upper quartile, minimum, maximum, and number of patients with an observation (N). Data will be split by time point where applicable.

Where there is missing data for an outcome variable, in the first instance, those records will be removed from any formal statistical analysis relating to that outcome variable, unless otherwise specified. In tabulations, numbers of missing observations will be provided, but percentages will not include them.

The main statistical analyses for primary and secondary outcomes will be adjusted for the minimisation variables: age, sex, baseline plasma troponin concentration unless doing so causes problems due to collinearity. Baseline troponin will be log transformed. Age and log baseline troponin will be adjusted for as a linear term, unless there is strong evidence of a departure from linearity for groups of related analyses. A group of related analyses is, e.g., the relationship between age and troponin, for all troponin analyses. This decision will be taken without looking at the unblinded treatment data, and taking care not to over-interpret smaller p-values in larger datasets, which may reflect the number of patients in the analysis rather than the magnitude of the effect. If a linear model is not adequate, then a fractional polynomial with two terms will be used. In general, analyses will be presented in subgroups of patients based on the presence of coronary 18F-fluoride uptake, and so this will not be adjusted for unless otherwise specified. The precise details of the minimisation variables are in the DIAMOND randomisation description document. Results of unadjusted statistical analyses will also be presented, although baseline measurements of outcome variables will always be adjusted for.

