### 7.1 Recruitment and retention, and definition of analysis populations

No formal statistical testing will be performed. The date of first and last patient randomised, and the number of patients randomised will be reported.

A CONSORT flow chart will be provided by the statistics team. Reasons for non-inclusion in the study (prior to randomisation) will be categorised. The number of patients discontinued early from the study will be summarised by reason for withdrawal and treatment. The number of patients in each treatment group will be specified for per protocol, and safety populations, with sufficient detail to explain why patients are excluded from each population.

The following will be presented:

- Number and percentage of patients who were ineligible for inclusion in trial (if any – it should not have been possible to randomise such patients).
- Numbers of patients who were randomised but never treated.
- Numbers of patients who received the opposite treatment to that allocated (if there are any)

- A listing of patients where the blind was broken early will be presented, including details of allocation, timing and reason for breaking blind, and outcome.

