### 7.3 Compliance

The number of patients who received <80%, 80-90%, >90% of their study medication, using pill counts, and the following formula.

$$\text{Compliance (\%)} = \frac{\text{Pill Taken}}{\text{Days} \times 2} \times 100$$

Note: Compliance will be calculated based on pill counts at visits. Days will be calculated as days from previous visit date to current visit date. Expected pill taken at visits will be days x2. If participant forgot to bring her/his pill boxes at 30 days visit but bring those at 3 months visits, compliance at 3 months will be used for 30 days compliance.

Reasons for compliance less than 80% will be provided if available.

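### No between-arm efficacy result is reported by random allocation, even as a sensitivity analysis, and the 30-day per-protocol exclusions also govern the 1-year CT outcomes

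*SAP*

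**What the plan says.** **Analysis sets.** SAP 5 defines two sets. The per-protocol set leaves out patients with no troponin sample, or with pill-count compliance under 80%, at the 30-day visit. The safety set is used for adverse events and bleeding. Per protocol is the default: "All analyses will be performed on the per protocol population unless otherwise specified". Within it, "Patients will be analysed according to treatment received".

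**Purpose.** SAP 6: "All analyses are seeking to show a difference, rather than equivalence or non-inferiority".

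**Protocol basis.** Protocol 9.2.1 introduces the exclusions thus: "For this primary analysis, we will exclude any patient who does not have a blood sample" (it goes on to add inadequate compliance, and leaves the required level to the SAP). Protocol 9.2.2 then turns to the other outcomes: "Similar analyses will be performed for the assessment of troponin at 30 days", continuing to 1-year troponin, calcium score and plaque volume without restating the set. As-treated grouping comes from protocol 5.5, on patients given the wrong treatment: "Given that this is a mechanistic study and not a clinical endpoint trial, they will be assigned to the treatment they actually received".

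**What is reported about exclusions.** SAP 7.1 gives numbers by arm and reasons for exclusion from each population, and "Numbers of patients who received the opposite treatment to that allocated (if there are any"). SAP 7.2 tabulates baseline data by allocated treatment for the per-protocol set and for everyone randomised. SAP 7.3 gives reasons for low compliance where available.

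**Compliance.** SAP 7.3 divides tablets taken by twice the number of days: "Days will be calculated as days from previous visit date to current visit date". If boxes are forgotten at 30 days but brought at 3 months, the 3-month figure stands in for the 30-day one.

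**The concern.** Whether a 30-day sample exists and how many tablets were taken are both settled after randomisation, and treatment may affect both. Protocol 12.6.2 itself names bleeding, breathlessness and bradyarrhythmia as risks of ticagrelor. A comparison restricted on such events no longer has the full protection of randomisation. In a trial that seeks a difference, the usual check is to repeat the comparison by allocation in everyone with the outcome measured. This plan contains no such check.

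The point is sharper at 1 year. A 30-day condition describes neither who was treated over the year nor who was scanned at the end of it, yet it decides who enters the calcium and plaque comparisons. Patients who withdraw before giving the 30-day sample leave the study and are replaced (protocol 5.6.6). The concern is therefore with patients who stay and have outcome data.

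**Working it through.** **1. Which set governs each between-arm efficacy analysis**

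| SAP section | Outcome | Set named there | Set that applies |
|---|---|---|---|
| 7.4 | Troponin at 30 days, uptake present | none | per protocol |
| 7.5.1, 7.5.2 | Troponin at 30 days, uptake absent; all patients | none | per protocol |
| 7.5.3 | Troponin AUC, 30 days to 1 year | none | per protocol, and last value present |
| 7.5.4 | Calcium score at 1 year | none | per protocol |
| 7.5.5 | Plaque calcium volume at 1 year | none | per protocol |

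SAP 7.5.6 and 7.5.7 are descriptive and not between-arm. Outside the baseline tables, all randomised patients are not analysed by allocation.

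**2. Three patients, each with baseline and 1-year CT**

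| | 30-day sample | 30-day compliance | After day 30 | In 7.5.4 and 7.5.5? |
|---|---|---|---|---|
| A | missing | 80% or more | takes drug all year | no |
| B | present | under 80% | takes drug all year | no |
| C | present | 80% or more | stops on day 31 | yes |

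**3. The 3-month stand-in (a separate, narrow point)**

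The protocol 7.2 schedule dispenses drug at day 0 and at 3 months, not at 30 days. Boxes first returned at 3 months therefore cover the whole period since day 0. Assume visits at days 30 and 91, two tablets a day, and a denominator running from day 0.

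- Expected tablets: 91 × 2 = 182. Threshold: 0.80 × 182 = 145.6, so 146 are needed.
- Full dosing from day 30 to day 91: 61 × 2 = 122. Needed from the first 30 days: 146 − 122 = 24 of 60, or 40%.
- Full dosing stopped at day 72: 144/182 = 79.1%, excluded, although the first 30 days were complete.

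Across the visit windows the minimum early dosing that passes runs from 8/50 = 16% (visits at days 25 and 105) to 40/70 = 57% (days 35 and 77). Behaviour after day 30 can thus decide entry to the 30-day analysis.

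**4. What an as-allocated analysis could lose to dilution**

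Inputs from protocol 9.1: means 7.89 and 3.95 ng/L (difference 3.94), SDs 9.34 and 1.89, two-sided 5%, 48 per arm, raised to 55.

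*Reproducing the plan.* Unequal-variance t with SE = √[(9.34² + 1.89²)/n]. At n = 48, SE = 1.375 and 3.94/1.375 = 2.86, giving power 80.2%; n = 47 gives 79.4%. So 48 is reproduced. At n = 55, SE = 1.285 and power is 85.4%.

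*As allocated.* Let a share f of the ticagrelor arm have no effect, so that they follow the placebo distribution.

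- Ticagrelor mean: 3.95 + 3.94f.
- Ticagrelor variance: (1 − f) × 1.89² + f × 9.34² + f(1 − f) × 3.94².
- Size: 55 per arm.
- Example, f = 10%: mean 4.344, difference 3.546, SD 3.65, SE 1.352, power 73.4%.

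*Per protocol.* Remove the same share from both arms, because SAP 5 excludes low compliers in either: n = 55(1 − f) per arm, with means and SDs as in protocol 9.1.

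| f (assumed) | As allocated | Per protocol | n per arm, per protocol |
|---|---|---|---|
| 1% | 84% | 85% | 54.5 |
| 5% | 80% | 84% | 52.3 |
| 10% | 73% | 81% | 49.5 |
| 20% | 60% | 77% | 44 |

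The shares are assumptions. The only related figure in the documents is the 1% who stopped study drug for breathlessness in the earlier acute coronary syndrome trial (protocol 12.6.2). The SAP models log troponin, so the table is illustrative.

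**The case against.** **The per-protocol primary analysis is a disclosed choice.** Protocol 9.2.1 sets it out, and protocol 5.5 gives a reason for as-treated grouping. That grouping changes nothing unless someone receives the wrong treatment, and SAP 7.1 counts such cases. This stands. A reader might infer that the SAP departs from the protocol on the primary outcome or that the primary analysis should be replaced. The documents support neither.

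**Carry-over to 1 year may be intended.** Protocol 9.2.1 describes only one set, and 9.2.2 then speaks of similar analyses. That is a natural reading, so this is an ambiguity that the SAP resolves one way and not a contradiction. It does not make a 30-day condition suitable for a 1-year scan.

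**Exclusions are reported.** It would be too strong to say that a reader learns nothing about who was left out. SAP 7.1 to 7.3 give numbers, reasons and baseline comparisons. None of them shows whether the treatment estimate moves.

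**The cut-offs of 90% and 80% do not conflict.** Protocol 6.5 uses 90% to define a deviation and gives no time window. Protocol 9.2.1 leaves the analysis cut-off to the SAP, and SAP 7.3 tabulates both. What remains is at most a clarification: neither protocol 6.5 nor SAP 7.3 says how interruptions permitted by protocol 5.6.5 count.

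**The stand-in may be rare.** It applies only when boxes are forgotten at 30 days and brought at 3 months, and the documents give no frequency. Read literally, with days counted from the previous visit, perfect dosing would score 182/122 = 149%, which suggests that reading is not intended. The result in step 3 does not depend on it.

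**The gain for the primary outcome is limited.** Patients with no 30-day sample are missing from both sets, so for SAP 7.4 the added analysis tests only the pill-count exclusion and the as-treated grouping. This also stands.

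**Conclusion.** The gap is real and worth closing. No between-arm efficacy result in SAP 7.4 to 7.5.5 is reported by random allocation, and 30-day conditions select the patients for the 1-year CT comparisons. It does not follow that any result will be biased by a particular amount: the documents give no exclusion rate and no outcomes for excluded patients, so neither size nor direction can be derived.

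The stand-in rule in SAP 7.3 is a genuine but narrow defect. With visits at days 30 and 91 and a day-0 denominator, 40% early dosing can pass and complete early dosing can fail. The number of patients affected is unknown.

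The as-allocated analysis could have less power than the per-protocol one, by about 1 percentage point at 1% non-effect and about 17 at 20%, on the raw-scale assumptions in step 4. That is a reason to report it beside the primary result, not instead of it.

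**What to change.** (a) Keep the protocol's per-protocol primary analysis. Add to SAP 5 an as-allocated set: all randomised patients with the relevant outcome measured, grouped by allocation, regardless of pill count, and labelled complete-case. Report it as a sensitivity analysis for SAP 7.4 and 7.5.1 to 7.5.3. For 7.5.3, state what happens when the 30-day value is missing, since the present rules cover only gaps between two values and missing final values.

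(b) For SAP 7.5.4 and 7.5.5, define the as-allocated set by having baseline and 1-year scans, not by 30-day sample or compliance. Treat any per-protocol result there as supportive.

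(c) In SAP 7.3, do not use a 3-month count as 30-day compliance unless it is computed from the dispensing date with the denominator stated. Otherwise treat 30-day compliance as missing under a stated rule. Reconcile protocol 5.6.5, protocol 6.5 and SAP 5 and 7.3 on how permitted interruptions count.

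The cost is SAP wording and one extra model per outcome, with no new data collection. SAP 6 already provides for an updated SAP. Outcome data will exist only for patients who continue study procedures (protocol 5.6.6). The downside is the possible dilution shown above.
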